4.4.5 Sensitivity Analyses

4.4.5.1 Loss to Follow-Up for Overall Survival Analyses

The impact of loss to follow-up on OS will be assessed depending on the number of patients who are determined to be lost to follow-up. If > 10% of patients are lost to follow-up for OS in either treatment arm, a sensitivity analysis will be performed for the comparisons between two treatment arms (i.e., Arm A vs. Arm C, Arm B vs. Arm C) in which patients who are lost to follow-up will be considered as having died at the last date they were known to be alive plus 1 day.

4.4.5.2 Missing Tumor Assessment

The impact of missing scheduled tumor assessments on PFS will be assessed depending on the number of patients who missed assessments scheduled immediately prior to the date of disease progression per RECIST v1.1 or the data cutoff. If > 5% of patients missed two or more assessments scheduled immediately prior to the date of disease progression per RECIST v1.1 or death in any treatment arm, the following sensitivity analysis will be performed:

- Patients who missed two or more scheduled assessments immediately prior to the date of disease progression per RECIST v1.1 or death will be censored at the last tumor assessment prior to the missed visits.

Statistical methodologies analogous to those used in the analysis of PFS as specified in Section 4.4.2 will be used for this sensitivity analysis.

4.4.6 Subgroup Analyses

The consistency of OS and PFS results will be examined in subgroups defined by demographic and baseline characteristics and stratification factors. Summaries of OS and PFS, including the unstratified HR estimated from a Cox proportional hazards model

and Kaplan-Meier estimates of median OS and PFS, will be produced separately for each level of the subgroup for the comparisons between two treatment arms and displayed in a Forest plot (Lewis and Clarke 2001). Kaplan-Meier plots of OS and PFS will also be produced for selected subgroups.

Summaries of ORR by subgroup will also be provided.

The subgroups to be considered include but are not limited to the following:

- Age (≤ 65 years, > 65 years) at randomization
- Race (non-White, White)
- Sex (female, male)
- Region (North America, Europe, Asia, Australia)
- Extended RAS mutation status (no, yes)
- MSI status (high, standard)
- PD-L1 status (high, low)
- Time since diagnosis of first metastasis (< 18 months, ≥ 18 months)
- ECOG performance status at randomization (0, 1)
- Location of the tumor in the colon (left colon, right colon)
- Liver metastases (no, yes)
- Previous treatment of any anti-epidermal growth factor receptor monoclonal antibodies (no, yes)
- Previous treatment of any anti-vascular endothelial growth factor therapies (no, yes)
- Number of previous treatment lines (3, > 3)

4.5 PHARMACOKINETIC AND PHARMACODYNAMIC ANALYSES

PK samples will be collected in this study as outlined in Appendix 3. Cobimetinib and atezolizumab maximum and minimum concentration data (C_{\max} and C_{\min} , respectively) will be tabulated and summarized (mean, standard deviation, median, range, coefficient of variation, geometric mean, and geometric mean coefficient of variation, as appropriate.

Additional PK analyses will be conducted, as appropriate, based on the availability of data.

Exploratory biomarker analyses will be performed in an effort to understand the association of these markers with study drug response, including efficacy and/or AEs. The blood and tumor biomarkers include but are not limited to mutational load by NGS, PD-L1 and CD8 as defined by IHC, or other methods. Additional pharmacodynamic analyses will be conducted as appropriate.

4.6 SAFETY ANALYSES

Unless specified otherwise, the safety analyses described below will be conducted for the safety population with patients grouped according to whether study treatment was received. Specifically, the treatment arm for safety analyses will be defined as follows:

- Cobimetinib + atezolizumab arm: patients who received any amount of cobimetinib
- Atezolizumab arm: patients who received any amount of atezolizumab without any amount of cobimetinib
- Regorafenib arm: patients who received any amount of regorafenib without any amount of either atezolizumab or cobimetinib

If a patient did not receive any amount of atezolizumab, cobimetinib, or regorafenib, the patient will not be included in the safety analyses.

4.6.1 Exposure of Study Medication

Study drug exposure, including treatment duration, number of cycles, and dose intensity, will be summarized for each treatment arm with descriptive statistics.

4.6.2 Adverse Events

Verbatim description of AEs will be mapped to MedDRA thesaurus terms and graded according to NCI CTCAE v4.0. All AEs that occur during or after the first study drug dose will be summarized by treatment arm and NCI CTCAE grade. In addition, serious adverse events (SAE), severe AEs (Grades 3, 4, and 5), AEs of special interest, and AEs leading to study drug discontinuation or interruption will be summarized accordingly. Multiple occurrences of the same event will be counted once at the maximum severity. The proportion of patients who experience at least one AE will be reported by toxicity term and treatment arm.

Listings of AEs will include all AEs with an onset that occurred on or after the first study drug treatment up to the data cutoff date.

Deaths reported during the study treatment period and those reported during the follow-up period after treatment discontinuation will be summarized by treatment arm.

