5.3.1 Adverse Event Reporting Period

Investigators will seek information on adverse events at each patient contact. All adverse events, whether reported by the patient or noted by study personnel, will be recorded in the patient's medical record and on the Adverse Event eCRF.

After informed consent has been obtained **but prior to initiation of study drug**, only serious adverse events caused by a protocol-mandated intervention (e.g., invasive procedures such as biopsies, discontinuation of medications) should be reported (see Section 5.4.2 for instructions for reporting serious adverse events).

After initiation of study drug, all *serious adverse events and Adverse Events of Special Interest, regardless of relationship to study drug, will be reported until 90 days after the last dose of study drug or initiation of new anti-cancer therapy, whichever occurs first. All other adverse events, regardless of relationship to study drug, will be reported until 30 days after the last dose of study drug or initiation of new anti-cancer*

therapy, whichever occurs first. Instructions for reporting adverse events that occur after the adverse event reporting period are provided in Section 5.6.

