5.6 POST-STUDY ADVERSE EVENTS

After the end of the reporting period for serious adverse events and adverse events of special interest (defined as 90 days after the last dose of study drug or initiation of a new anti-cancer treatment whichever comes first), all deaths, regardless of cause, should be reported through use of the Long-Term Survival Follow-Up eCRF. In addition, if the investigator becomes aware of a serious adverse event that is believed to be related to prior study drug treatment, the event should be reported through use of the Adverse Event eCRF.

5.7 EXPEDITED REPORTING TO HEALTH AUTHORITIES, INVESTIGATORS, INSTITUTIONAL REVIEW BOARDS, AND ETHICS COMMITTEES

The Sponsor will promptly evaluate all serious adverse events and adverse events of special interest against cumulative product experience to identify and expeditiously communicate possible new safety findings to investigators, IRBs, ECs, and applicable health authorities based on applicable legislation.

To determine reporting requirements for single adverse event cases, the Sponsor will assess the expectedness of these events using the following reference documents:

- Cobimetinib Investigator's Brochure
- Atezolizumab Investigator's Brochure
- *Summary of Product Characteristics (SPC) for regorafenib (Stivarga® SPC 2017)*

The Sponsor will compare the severity of each event and the cumulative event frequency reported for the study with the severity and frequency reported in the applicable reference document.

Reporting requirements will also be based on the investigator's assessment of causality and seriousness, with allowance for upgrading by the Sponsor as needed.

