2.3 DETERMINATION OF SAMPLE SIZE

The study will randomize approximately 360 patients, including a minimum of 180 patients with extended RAS-mutant mCRC (assuming a prevalence of at least 50%), to cobimetinib plus atezolizumab (Arm A), atezolizumab monotherapy (Arm B), and regorafenib (Arm C) with the randomization ratio of 2:1:1, respectively.

The type 1 error (α) for the analysis of the primary endpoint of OS in the comparison of Arm A versus Arm C (the control arm) is 0.05 (2-sided). If OS is statistically significant in the comparison of Arm A versus Arm C, then the OS comparison of Arm B versus Arm C will be tested at a 2-sided α -level of 0.05.

The overview of the type 1 error (α) control is shown in [Figure 2](#).

Figure 2 Overview of Hierarchical Testing Sequence for Type 1 Error^a Control (2-Sided)

OS=overall survival

^a OS will be tested at a 2-sided significance level $\alpha=0.05$ only if the result of previous testing is positive (i.e., statistically significant).

The sample size of this study is determined on the basis of the number of events required to demonstrate efficacy with regard to OS in both comparisons (Arm A vs. Arm C and Arm B vs. Arm C).

The estimate of the number of events required to demonstrate efficacy with regard to OS is based on the following assumptions:

- Two-sided significance level of 0.05
- Arm A versus Arm C: 87% power to detect an hazard ratio (HR) of 0.61, corresponding to an improvement in median OS from 6.4 months in Arm C to 10.5 months in Arm A
- Arm B versus Arm C: 80% power to detect an HR of 0.61, corresponding to an improvement in median OS from 6.4 months in Arm C to 10.5 months in Arm B
- No interim analysis for OS

- Dropout rate of 10% in 24 months
- Hierarchical testing of Arm A versus Arm C followed by Arm B versus Arm C to control the overall α level of 5%

With these assumptions, approximately 360 patients in total will be randomized into this study, with approximately 270 patients for the comparison of Arm A versus Arm C and approximately 180 patients for the comparison of Arm B versus Arm C. The OS final analysis will be conducted when there are approximately 235 deaths occurring from all three arms. At this time, it is expected that approximately 178 deaths for the comparison of Arm A versus Arm C and approximately 127 deaths for the comparison of Arm B versus Arm C will have occurred.

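### AEs are summarised only as crude proportions over windows set by time on treatment, so any between-arm difference in treatment duration, in either direction, distorts the comparison for AEs that keep accruing

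*SAP*

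**What the plan says.** SAP 4.6.2 tabulates AEs by arm and CTCAE grade, with separate summaries of serious, Grade 3 to 5, special-interest and discontinuation-related events. The counting unit is the patient: "Multiple occurrences of the same event will be counted once at the maximum severity". The measure by arm is a proportion: "The proportion of patients who experience at least one AE will be reported by toxicity term and treatment arm". Protocol 6.6 plans the same.

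Collection is limited in time by Protocol 5.3.1. For non-serious events outside the special-interest list: "All other adverse events, regardless of relationship to study drug, will be reported until 30 days after the last dose of study drug", or until new anti-cancer therapy if that is earlier. SAEs and AESIs "will be reported until 90 days after the last dose of study drug or initiation of new anti-cancer therapy, whichever occurs first". After that, Protocol 5.6 keeps deaths, plus the case "if the investigator becomes aware of a serious adverse event that is believed to be related to prior study drug treatment"; the Appendix 1 footnotes extend this to related AESIs.

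Treatment has no planned length. Protocol 3.1 continues it to progression, unacceptable toxicity, death, withdrawal or pregnancy, and 4.3.2.4 allows it past progression in every arm.

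Exposure is handled on its own in SAP 4.6.1: "Study drug exposure, including treatment duration, number of cycles, and dose intensity, will be summarized for each treatment arm with descriptive statistics". Neither document plans an AE rate per unit of time at risk, a time-to-first-AE analysis or a common fixed AE window. The safety objective (Protocol 2.2) is framed as a comparison with regorafenib.

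**The concern.** A patient treated for six months is observed for AEs for about seven; a patient treated for six weeks is observed for about ten weeks. If one arm has more patients of the first kind, its crude proportion rises for any event that can occur throughout treatment, even when the monthly risk is identical. The arm treated for less time gains the opposite advantage, and early stopping can hide toxicity.

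The protocol gives reasons to think windows could differ. The rationale for treating past progression (3.3.8) is specific to immunotherapy, although the permission covers all arms. In Arm A one drug may continue after the other is stopped (Table 4 in 5.1.4.2), which delays the last dose; single-agent Arm C has no equivalent. Conversely, toxicity of the combination could shorten treatment in Arm A. At stake is the descriptive benefit-risk comparison with regorafenib, not a hypothesis test.

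**Working it through.** **The plan's own figures.** The documents state no AE rate and no treatment duration. The only planned between-arm ratio is for OS (SAP 2.3): "corresponding to an improvement in median OS from 6.4 months in Arm C to 10.5 months in Arm A", that is 6.4/10.5 = 0.610. Its design figures reproduce (Schoenfeld, two-sided 0.05, event allocation 2/3 and 1/2):
- A vs C, 178 deaths: power 87.5% (stated 87%); minimum detectable HR exp(−1.96/√(178 × 2/3 × 1/3)) = 0.732 (stated 0.73).
- B vs C, 127 deaths: power 79.5% (stated 80%); minimum detectable HR exp(−1.96/√(127 × 1/4)) = 0.706 (stated 0.71).

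**Assumptions for the AE illustration**, none of them in the documents: exponential time on treatment T with mean m = median/ln 2; Arm C median 1.5 to 3 months; the same constant AE hazard λ in both arms; every patient observed for the full tail w after last dose (1 month, or 3 months for SAEs and AESIs).

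**Formula.** The expected crude proportion is 1 − E[exp(−λ(T + w))] = 1 − exp(−λw)/(1 + λm). Solve λ so that Arm C shows 30%, then divide m by 0.9, 0.8 or 0.61 for the longer-treated arm.

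**Example, Arm C median 2 months, w = 1.** m = 2/0.693 = 2.885 and λ = 0.1010.
- Arm C: 1 − 0.9039/(1 + 0.1010 × 2.885) = 30.0%.
- Ratio 1/0.8 (m = 3.607): 1 − 0.9039/1.364 = 33.7%.
- Ratio 1/0.61 (m = 4.730): 1 − 0.9039/1.478 = 38.8%.

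**Proportion in the longer-treated arm when Arm C shows 30%:**

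| Tail | Arm C median (months) | Ratio 1/0.9 | Ratio 1/0.8 | Ratio 1/0.61 |
|---|---|---|---|---|
| 30 days | 1.5 | 31.6% | 33.5% | 38.3% |
| 30 days | 2 | 31.7% | 33.7% | 38.8% |
| 30 days | 3 | 31.9% | 34.0% | 39.5% |
| 90 days | 1.5 | 31.0% | 32.3% | 35.5% |
| 90 days | 2 | 31.2% | 32.6% | 36.3% |
| 90 days | 3 | 31.4% | 33.1% | 37.3% |

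**Reverse direction.** If the experimental arm is treated for 0.61 times as long (m multiplied by 0.61, 30-day tail), 30% in Arm C becomes 22.6% to 23.8%. With equal durations there is no change.

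**Early-onset AEs.** With the hazard confined to month 1 and mean treatment of 2 against 3.28 months (2 × 10.5/6.4), the difference is about 0. Confined to the first 2 months, it is 1.1 to 1.7 points.

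**Check on patient-month rates.** Take an AE confined to month 1 with 30% incidence in both arms, so λ = −ln 0.7 = 0.357 in that month. Mean time to first event or window end is 0.3/0.357 + 0.7m = 0.841 + 0.7m. At a ratio of 1/0.61:
- Arm C median 1.5: 2.356 against 3.324 months, rate ratio 0.71.
- Arm C median 3: 3.871 against 5.808 months, rate ratio 0.67.

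So the rate makes the longer-treated arm look safer although incidence is equal.

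**The case against.** The tempting stronger reading is that a trial designed for a survival benefit must show inflated toxicity in the experimental arms. The documents do not support it. They plan an OS ratio, not a treatment-duration ratio, and treatment normally stops at progression or toxicity. The one pair of figures in the protocol points away from it: section 3.3.6 cites a regorafenib trial with a 1.4-month OS gain but a 0.3-month PFS gain. Arm A could equally be treated for less time. The 38% to 40% figure is therefore the top of the range, not the expectation.

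The other arguments carry weight too. The AE analysis has no test, so no error rate is affected. A crude proportion legitimately answers what share of treated patients had the event on the regimen. SAP 4.6.1 would show unequal duration by arm, and SAP 4.6.3 summarises laboratory data over time. Replacing the proportions with patient-month rates would introduce a bias of its own for early events, as shown above.

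What remains is that a separate exposure table does not let a reader recover time at risk to first event for a given AE. For accruing AEs the reader cannot tell a difference in toxicity from a difference in observation time.

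**Conclusion.** The point holds in a conditional, two-sided form. AE windows depend on open-ended treatment, the planned summary is crude, and nothing in either document adjusts for unequal time at risk. For an AE seen in 30% of Arm C at the same true rate, the spurious excess in the longer-treated arm is about 2, 4, and 8 to 10 points at duration ratios of 1/0.9, 1/0.8 and 1/0.61 with the 30-day tail. With the 90-day tail it is about 1, 2 to 3, and 5.5 to 7 points. These sizes rest on assumed durations, exponential treatment time and a constant hazard, and they ignore early closure of the window by new therapy or death, which could widen or narrow the gap. The sign reverses if the experimental arm stops earlier.

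This is a problem of interpreting descriptive output, and it invalidates no planned inference. It ranks between a suggestion and a recommended change.

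**What to change.** In SAP 4.6.2 keep the crude proportions. Beside them, for all AEs, Grade 3 to 5 AEs, SAEs, AESIs and AEs leading to discontinuation, add:

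1. Cumulative incidence of first event at fixed times, for example 8 and 16 weeks, by the Aalen-Johansen method, with death as a competing event and censoring at the end of the Protocol 5.3.1 window.
2. As a supplement only, incidence per 100 patient-months at risk, from first dose to first event or window end.

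State two caveats in the text. The rates assume a roughly constant hazard and can favour the longer-treated arm for early-onset AEs. Censoring at window end may be informative, because windows close through toxicity, progression or new therapy.

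The cost is SAP wording and one extra table set, using dates the trial already collects, together with the burden of explaining these caveats. Specifying it before arm-level results are known avoids a later choice of safety measure.

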4.6.3 Laboratory Data

Laboratory data will be summarized over time including change from baseline by treatment arm. Values outside the normal ranges will be summarized. Additionally, selected laboratory data will be classified in accordance with NCI CTCAE v4.0 and will be summarized by grade and treatment arm. Highest NCI CTCAE grade post-baseline will also be reported, and shift tables from baseline to worst value during the study post-baseline will be presented.

4.6.4 Vital Signs

Changes in selected vital signs will be summarized by treatment arm and by change over time including change from baseline.

ECOG performance status will also be summarized over time.

4.7 IMMUNOGENICITY ANALYSES

The number and percentage of patients with positive serum antibodies to atezolizumab at baseline and postbaseline during the study period will be summarized. Adverse events occurring in patients with positive serum antibodies to atezolizumab will be reviewed. The relationship of the immunogenicity response with pharmacokinetics, safety, and efficacy may also be evaluated when appropriate.

ATA sampling timepoints are provided in [Appendix 3](#).

4.8 MISSING DATA

Please refer to Sections [4.4.1](#) and [4.4.2](#) for methods of handling missing data for the primary and secondary efficacy endpoints.

4.9 EXPLORATORY ANALYSES

Exploratory efficacy endpoints defined in the protocol other than the analyses specified in Section [4.4.3](#) are outside of the scope of this SAP and will not be included in the CSR.

Appendix 1 Protocol Synopsis

PROTOCOL SYNOPSIS

TITLE:	A Phase III, open-label, multicenter, three-arm, randomized study to investigate the efficacy and safety of cobimetinib plus atezolizumab and atezolizumab monotherapy vs. regorafenib in patients with previously treated unresectable locally advanced or metastatic colorectal adenocarcinoma
PROTOCOL NUMBER:	GO30182
VERSION NUMBER:	4
EUDRACT NUMBER:	2016-000202-11
IND NUMBER:	130,091
TEST PRODUCT:	Cobimetinib (RO5514041); atezolizumab (RO5541267)
PHASE:	III
INDICATION:	Previously treated unresectable locally advanced or metastatic colorectal adenocarcinoma
SPONSOR:	F. Hoffmann-La Roche Ltd

Objectives and Endpoints

Primary Efficacy Objective

The primary efficacy objective for this study is to evaluate the efficacy of cobimetinib plus atezolizumab compared to regorafenib (standard of care) in patients with previously treated, unresectable locally advanced or metastatic colorectal cancer (CRC) on the basis of overall survival (OS). Atezolizumab monotherapy will also be evaluated compared to regorafenib on the basis of OS.

Secondary Efficacy Objectives

The secondary efficacy objectives include:

- Investigator-assessed progression-free survival per Response Evaluation Criteria in Solid Tumors (RECIST) v1.1 of patients in the cobimetinib plus atezolizumab arm and the atezolizumab monotherapy arm compared to the regorafenib arm.
- Investigator-assessed objective response rate per RECIST v1.1 of patients in the cobimetinib plus atezolizumab arm and atezolizumab monotherapy arm compared to the regorafenib arm
- Duration of response of patients in the cobimetinib plus atezolizumab arm and atezolizumab monotherapy arm compared to the regorafenib arm
- Impact on functioning as measured by changes from baseline on the five-item physical functioning sub-scale of the patient-completed European Organization for Research and Treatment of Cancer Quality of Life Core 30 questionnaire (EORTC QLQ-C30)
- Impact on health-related quality of life as measured by changes from baseline on the two-item global health status/quality of life sub-scale of the EORTC QLQ-C30

Appendix 1

Protocol Synopsis (cont.)

Safety Objective

The safety objective for this study is to evaluate the safety profile and adverse events encountered by patients in the cobimetinib plus atezolizumab arm and atezolizumab monotherapy arm compared to the regorafenib arm.

Pharmacokinetic Objective

The PK objective for this study is to characterize the cobimetinib and atezolizumab PK profiles on the basis of the following:

- Plasma concentration of cobimetinib at timepoints specified in Appendix 2
- Serum concentration of atezolizumab in both the cobimetinib plus atezolizumab arm and the monotherapy atezolizumab arm at timepoints specified in Appendix 2

Immunogenicity Objective

The immunogenicity objective for this study is to evaluate the immune response to atezolizumab on the basis of the following endpoint:

- Incidence of anti-therapeutic antibodies (ATAs) during the study relative to the prevalence of ATAs at baseline in both the cobimetinib plus atezolizumab arm and the atezolizumab monotherapy arm.

The exploratory immunogenicity objective for this study is to evaluate potential effects of ATAs on efficacy, safety, or pharmacokinetics.

Biomarker Objectives

The exploratory biomarker objectives for this study are as follows:

- To assess the following molecular characteristics in tumor samples during pretreatment, on treatment, and at progression:
 - Genetic profile including but not limited to somatic mutations and microsatellite (MSI) status or mutation load as identified through next-generation sequencing or other genetic analysis.
 - Immune contextures, such as programmed death-ligand 1 (PD-L1), CD8 T cells or major histocompatibility complex expression, as identified by immunohistochemistry and gene signature profiling
 - CRC molecular subtyping as defined by genetic and RNA and protein profiles
- To evaluate the relationship between circulating tumor biomarkers (including but not limited to carcinoembryonic antigen [CEA], tumor-associated mutations in cell-free DNA) and measures of efficacy

Patient-Reported Outcomes Objectives

The additional patient-reported outcome objective of the study is to assess treatment impact and disease symptoms from the sub-scales of the EORTC QLQ-C30 that assess diarrhea, constipation, lack of appetite, fatigue, and two additional items from the EORTC item bank that assess bloating and abdominal pain associated with cobimetinib plus atezolizumab compared with regorafenib in patients with metastatic CRC (mCRC).

Pharmacoeconomic Objectives

In addition, a study objective is to obtain general measures of health as measured by the EuroQoL 5 Dimensions questionnaire for health economic modeling of cobimetinib plus

